6.2.1 Adverse events

An AE is any undesirable sign, symptom, or medical condition occurring after signing the ICF. Information about all AEs, regardless of seriousness or relationship to study treatment, whether volunteered by the subject, discovered by questioning, or detected through physical examination, laboratory testing, or other means, will be collected and recorded on the AE eCRF page and followed as appropriate.

Medical conditions present prior to study entry will be documented in the Medical History eCRF. However, medical conditions occurring after signing the ICF are to be recorded as AEs. Treatment-emergent adverse events (TEAEs) are defined as AEs with onset after the first dose of study drug or existing AEs that worsened after the first dose of study drug until the last administration of study medication plus 10 weeks follow up.

The Investigator (or delegate) is obliged to interview subjects at each visit and clarify/discuss any abnormality that may indicate a potential AE.

Subjects should be encouraged to report AEs that occur between scheduled visits to the Investigator or between home injections to the nurse.

AEs will be recorded from the time of signing the ICF until the end of the safety follow-up. If any AE is ongoing at the time of subject withdrawal, the subject will be asked to return for clinic visits or to respond to follow-up by telephone (if the AE is considered not related or unlikely related to study drug) until resolution or stabilization of this AE.

Whenever possible, diagnosis or single syndrome should be reported instead of symptoms. The Investigator should specify the date of onset, intensity, action taken with respect to study treatment, corrective treatment/therapy given, additional investigations performed, outcome, and his/her opinion as to whether there is a reasonable possibility that the AE was caused by the study treatment. When AEs occur on the day of study drug administration, the approximate time of day should be provided.

Any AE that occurs during the study must be monitored and followed up until one or more of the following criteria have been met:

- It has resolved to \leq Grade 1 or baseline level
- Pathological laboratory findings have returned to normal
- Steady state has been achieved

A subset of AEs will be closely monitored (ie, events identified as AESIs; see [Section 6.2.2](#) and [Table 3](#)).

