7.2.4 Safety analysis

The summary of safety results will be presented by treatment group. All safety analyses will be performed on the Safety Population. The baseline value is defined generally as the last available value before randomization. The treatment-emergent adverse event (TEAE) period is defined as the time between the first administration of study medication to the last administration of study medication plus 10 weeks follow up.

Adverse events will be presented by System Organ Class (SOC) and Preferred Term (PT) for each treatment group, the number (n) and percentage (%) of subjects experiencing an AE. The numbers and percentages of subjects with at least one TEAE, treatment-emergent SAE, TEAE leading to death, and TEAE leading to permanent treatment discontinuation will be tabulated by treatment group. In addition, TEAEs will be described according to maximum intensity and relation to the study drug.

- The following deaths summaries will be generated
Death in nonrandomized subjects or randomized and not treated subjects
- Treatment-emergent AE leading to death (death as an outcome on the AE eCRF page as reported by the Investigator) by primary SOC, HLG, HLT, and PT showing number (%) of subjects sorted by internationally agreed order of SOC and alphabetic order of HLG, HLT, and PT
- ACSI will be summarized by treatment group

Results and change from baseline for the laboratory parameters will be summarized by treatment group for baseline and each post baseline time point, endpoint, minimum and maximum value. Summary statistics will include number of subjects, mean, standard deviation, median, Q1, Q3, minimum, and maximum.

The following definitions will be applied to laboratory parameters.

- The potentially clinically significant abnormality (PCSA) values are defined as abnormal values considered medically important by the Sponsor according to predefined criteria/thresholds based on literature review and defined by the Sponsor for clinical laboratory tests.

- PCSA criteria will determine which subjects had at least 1 PCSA during the on-treatment period, taking into account all evaluations performed during the on-treatment period, including unscheduled or repeated evaluations. The number of all such subjects will be the numerator for the on-treatment PCSA percentage.

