The proportion of subjects who had at least one incidence of PCSA at any time during the TEAE period will be summarized by treatment group. Shift tables showing changes with respect to the baseline status will be provided. Vital signs, ECG and physical examinations will be summarized using descriptive statistics.

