4 STATISTICAL ANALYSES

4.1 GENERAL CONSIDERATIONS

For the analyses for the primary, secondary and tertiary/exploratory objectives, the corresponding analyses population are summarized in [Table 2](#) and [Table 5](#), and the analyses period is on the double blind placebo-controlled period.

However, the analyses for placebo controlled and open label treatment period combined are discussed in [Section 4.8.5](#).

Observation period

The observation period will be divided into the following segments:

The **pre-treatment period** is defined as the time from the signed informed consent (and ascent for adolescent in Stage 2) date up to the first administration of the IMP.

For the **placebo-controlled treatment period**, the treatment-emergent (TE) period is defined as the period from the first IMP administration to

- the first administration of the IMP in open-label extension period for participants who entered open-label extension period or,
- the last administration of the IMP + 7 days if the participant is ongoing or not continuing in open-label treatment extension period (eg, early discontinuation of treatment).

For the **lademirsen treatment period**, the TE period is defined as the period from the first lademirsen administration the last administration of lademirsen + 7 days. The period is defined for participants who had at least 1 full or partial administration of lademirsen.

For the **overall study period**, the TE period is defined as from the first IMP administration to the last administration of the IMP + 7 days.

For the **post-treatment period**, it is defined as the period from the end of overall study TE period until the end of the study (eg, the later day of the last scheduled visit, or the end-of-study date collected on e-CRF page “Completion of End of Study/Follow-up”. If death is the end-of-study reason, date of death will be used.)

The TE period and on-treatment period are defined the same, therefore, the wording may be used interchangeably.

The lademirsen treatment period and overall study period are used for analysis in [Section 4.8.5](#).

In general, for analysis in the **placebo-controlled treatment period**, the baseline is the last available value prior to first IMP. For analysis in the **lademirsen treatment period**, the baseline is the last available value prior to the first administration of lademirsen.

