 - Treatment-emergent adverse event leading to permanent treatment discontinuation.
- All treatment-emergent adverse events, by primary SOC and PT, showing number (%) of participants with at least 1 treatment-emergent adverse event, sorted by internationally

agreed order of primary SOC and by decreasing incidence of PTs within each SOC will be presented.

- All treatment-emergent adverse events related to IMP, by primary SOC and PT, showing the number (%) of participants with at least 1 treatment-emergent adverse event, sorted by internationally agreed order of primary SOC and by decreasing incidence of PTs within each SOC will be presented.
- All treatment-emergent adverse events, by maximal severity, presented by primary SOC and PT, showing the number (%) of participants with at least 1 treatment-emergent adverse event by severity (ie, mild, moderate, or severe), sorted by the internationally agreed SOC order and by decreasing incidence of PTs within each SOC will be presented.
- A listing of all treatment-emergent adverse events during the overall study period will be presented.

Analysis of all treatment-emergent serious adverse event(s)

- All treatment-emergent serious adverse events by primary SOC and PT, showing number (%) of participants with at least 1 serious treatment-emergent adverse event, sorted by internationally agreed order of primary SOC and by decreasing incidence of PTs within each SOC will be presented.
- All treatment-emergent serious adverse events related to IMP by primary SOC and PT, showing the number (%) of participants with at least 1 serious treatment-emergent adverse event, sorted by internationally agreed order of primary SOC and by decreasing incidence of PTs within each SOC will be presented.
- A listing of all treatment-emergent serious adverse events during the overall study period will be presented.

Analysis of all treatment-emergent adverse event(s) leading to permanent treatment discontinuation

- All treatment-emergent adverse events leading to permanent treatment discontinuation showing the number (%) of participants with permanent treatment discontinuation due to treatment-emergent adverse event, sorted by internationally agreed order of primary SOC and by decreasing incidence of PTs within each SOC will be presented.
- TEAEs leading to permanent treatment discontinuation will be indicated in the listing of TEAEs.

Analysis of all treatment-emergent adverse event(s) leading to dose reduction

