- All treatment-emergent adverse events leading to dose reduction in placebo-control treatment period showing the number (%) of participants with dose reduction due to treatment-emergent adverse event sorted by internationally agreed order of primary SOC and by decreasing incidence of PTs within each SOC will be presented.
- TEAE leading to dose reduction will be indicated in the listing of TEAEs.

Analysis of all treatment-emergent adverse events of special interest (AESI)

- All treatment-emergent AESIs identified by investigator (eg, through eCRF) in placebo-control treatment period showing the number (%) of participants by PT, sorted by the decreasing incidence of PT will be presented.
- AESIs identified by investigator will be indicated in the listing of TEAEs.

Analysis of treatment-emergent injection site reaction (ISR)

- Number (%) of participants with treatment emergent injection site reactions by PT by grade/maximal intensity will be provided.

Note: If more than one ISR records (eg, when the ISR grading is \geq None [Grade 0]) corresponding to the same adverse event (eg, when the AE code is same) as collected in eCRF, they will be considered as one ISR adverse event during the analysis.

Analysis of post-treatment adverse events

- A listing of all adverse events during the post-treatment period may be presented.

Deaths

- A listing of all adverse events leading to death during the study will be presented if any.

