4.7.3 Laboratory variables, vital signs and electrocardiograms (ECGs)

The summary statistics (including number, mean, median, Q1, Q3, standard deviation, minimum and maximum) of all laboratory variables (central laboratory values and changes from baseline) based on availability will be calculated for each visit or study assessments (baseline, each post-baseline time point, last on-treatment during placebo-controlled treatment period and lademirsen treatment period respectively, and worst on-treatment value during placebo-controlled treatment period and lademirsen treatment period respectively) by treatment group during the overall study period.

For selected laboratory parameters (eg, platelet, creatinine, proteinuria [protein/creatinine ratio], albumin/creatinine ratio, eGFR, and selected parameters in liver function), individual participant plots will be prepared for the observed value overtime during overall study period. For selected kidney parameters (eg, cystatin C, and blood urea nitrogen), mean (+/-SE) plots will be prepared for the observed value over time during the double-blind period, and also by screening eGFR stratification factor.

The incidence of PCSAs at any time during the placebo-control treatment-emergent period and lademirsen treatment-emergent period, respectively, will be summarized by biological function and treatment group whatever the baseline level is.

For PCSA analyses, the laboratory measurements obtained at either scheduled or unscheduled visits should be used; and, both the centralized and local test results should be used, as long as their available dates/time is different from each other's. Centralized data will be used

preferentially to the local measures in the PCSA analyses when measurements are performed on the same date and at the same time for a given laboratory test.

Listing of PCSAs during the overall study period will be provided.

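### The SAP closes the treatment-emergent window 7 days after the last dose and the approved protocol closes it 10 weeks after; the addendum neither reconciles nor declares the difference

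*SAP*

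**What the plan says.** **Protocol.** Section 7.2.4 runs the TEAE period from the first dose to "the last administration of study medication plus 10 weeks follow up". Section 6.2.1 defines a TEAE the same way: onset or worsening after the first dose, "until the last administration of study medication plus 10 weeks follow up".

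**SAP 4.1.** For participants who enter the extension, the placebo-controlled treatment-emergent period stops at the first open-label dose. For everyone else it stops at "the last administration of the IMP + 7 days if the participant is ongoing or not continuing in open-label treatment extension period". The lademirsen and overall study periods also end 7 days after the last dose. What follows is post-treatment. The section treats the treatment-emergent and on-treatment periods as the same thing.

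**SAP 4.7.2.** TEAEs are defined by those periods. The TEAE and SAE tables are confined to them, as are the committed listings, for example: "A listing of all treatment-emergent serious adverse events during the overall study period will be presented". For later events the SAP offers only this: "A listing of all adverse events during the post-treatment period may be presented". AEs leading to death have a committed listing for the whole study.

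**Addendum.** Section 1 says that SAP version 2.0 was built on Amended Protocol 13, that this amendment was withdrawn from health-authority submission, and that Amended Protocol 11 (12 in France) is the latest approved version. Section 3 reports no major change of method and cuts most safety analyses to Week 48. Table 1 keeps TEAE and SAE incidence for the placebo-controlled and lademirsen periods. The window is not mentioned.

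**The concern.** Safety and tolerability is a primary objective under Amended Protocols 11 and 12, as footnote c to the addendum's Table 1 acknowledges. TEAE and SAE tables built from the SAP would not follow the TEAE definition in the approved protocol, and a reader of the study report would not be told so. A non-fatal SAE that starts on day 20 after the last dose is treatment-emergent under the protocol. Under the SAP it has no guaranteed place in any table or listing.

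The addendum was an opportunity to settle this. Its section 3.1 restores a different analysis expressly to bring the plan back into line with Amended Protocols 11 and 12.

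**Working it through.** The plan gives no figure to reproduce. The check compares two definitions and then does date arithmetic.

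**1. Where an event goes, by day of onset after the last dose (participant not entering the extension, or after the final lademirsen dose)**

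| Onset | Protocol 6.2.1 and 7.2.4 | SAP 4.1 and 4.7.2 |
|---|---|---|
| Days 1–7 | TEAE | TEAE: tables and committed listings |
| Days 8–70 | TEAE | Post-treatment: optional listing only, unless the AE leads to death |
| After day 70 | Not a TEAE | Post-treatment: as above |

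**2. Size of the gap.** Protocol tail: 10 × 7 = 70 days. SAP tail: 7 days. Difference: 70 − 7 = 63 days, and 63/70 = 90% of the post-dose window.

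**3. Share of the whole protocol TEAE period.** For a last dose at Week w, the share is 63/(7w + 70):
- Week 24: 63/238 = 26%
- Week 47: 63/399 = 16%
- Week 95: 63/735 = 9%

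These are shares of time, not of events. Week 95 follows Protocol 5.3, which gives no injection at Week 96. Table 2 of the protocol marks one there, and the two places should be reconciled. The choice hardly matters here: 63/742 = 8.5% against 8.6%.

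**4. Effect of the Week 48 limit, if it also truncates follow-up.** Post-dose days available are min(70, 336 − 7w). Subtracting the 7 that the SAP keeps gives the days in dispute:
- w ≤ 38: 70 − 7 = 63
- w = 42: 42 − 7 = 35
- w = 46: 14 − 7 = 7
- w = 47: 7 − 7 = 0

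So the limit can shrink the gap for late last doses. It does not explain a 7-day rule for earlier ones.

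**5. Who is affected.** In the placebo-controlled tables, only participants who do not enter the extension. In the lademirsen-period tables, everyone after the final lademirsen dose. The addendum says the study ended before all Stage 1 participants had completed the double-blind period, so those outside the extension are not only ordinary drop-outs. Their number is not given.

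**6. Comparability of the windows.** Participants who roll over have a nominal 7 days between the Week 47 dose and the first open-label dose at Week 48 (3 to 11 days with ±2-day windows at both visits). Under the 10-week rule, participants who do not roll over would have 70 days. Under the 7-day rule the two are nearly equal.

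**The case against.** The strongest reply is that SAP version 2.0 was written for Amended Protocol 13, which is not among the documents and may itself use 7 days. The addendum openly sets out to explain the effect of following that amendment, and Protocol 7.2 calls itself a summary. In addition, 7 days is one dosing interval and gives nearly equal post-dose windows (step 6). With 10 weeks, crude incidence in the placebo-controlled tables could be distorted if discontinuation differs by arm.

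Much of this stands. Seven days is a defensible window. What does not stand is leaving the difference undeclared: by the addendum's own account Amended Protocol 13 was not the approved version, and a general reference to it does not tell a reader that the TEAE definition has changed.

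The reach is also limited:
- Participants who roll over lose nothing in the placebo-controlled tables.
- SAP 5.3 treats AEs with missing or partial onset dates as treatment-emergent unless the available date information shows otherwise.
- AEs leading to death are listed for the whole study.
- AEs are recorded to the end of safety follow-up (Protocol 6.2.1), and Protocol 9.2.5 obliges the sponsor to report all safety observations in the study report. That general duty does not correct the tables or make the listing mandatory.

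A reader might also infer that the laboratory abnormality (PCSA) tables breach the protocol in the same way. The documents do not support that. Protocol 7.2.4 is itself mixed: it determines "which subjects had at least 1 PCSA during the on-treatment period" and then summarises "at least one incidence of PCSA at any time during the TEAE period". The early-termination visit, at which blood count, chemistry and coagulation may not be skipped, falls 7 ± 2 days after the last visit. If the last dose was given at that visit, a panel on days 5 to 7 still counts. The PCSA window needs stating, but it is an ambiguity.

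**Conclusion.** The point holds as an undeclared departure from the approved TEAE definition and should be fixed. AEs and non-fatal SAEs with onset on days 8 to 70 after the last dose, 63 of 70 post-dose days, miss the TEAE and SAE tables and the committed listings.

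This rests on two readings: that SAP 4.1 still governs because the addendum does not change it, and that Amended Protocols 11 and 12 are the reference because the addendum names them as approved. If the Week 48 limit truncates follow-up, the gap within that limit shrinks for last doses after Week 38 and reaches zero at Week 47.

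Three stronger inferences go too far:
- **That a known or large share of events is lost.** The documents give no event counts, and the percentages in step 3 are of time. No data are lost.
- **That the 10 weeks was chosen on safety-analysis grounds and then overridden.** The history for Amended Protocol 09 gives only harmonization of follow-up and clarification as reasons.
- **That the number of participants unable to reach Week 48 can be worked out from calendar dates.** SAP 1.1 gives only an upper bound for the end of randomization and no first-dose dates.

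**What to change.** By addendum, before the final database lock:

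1. **Window.** Preferably end the treatment-emergent period at last IMP plus 10 weeks for the TEAE and SAE tables and listings. Keep the cut at the first open-label dose for roll-over participants in the placebo-controlled period. Show the 7-day window as a supplementary table, because its post-dose windows are nearly equal between roll-over and other participants. Alternatively, keep 7 days as the main window, declare it as a departure from Amended Protocols 11 and 12 with the reason, and add a 10-week table.
2. **Listing.** In either case change the post-treatment AE listing, SAEs included, from *may* to *will*.
3. **Clarifications.** State whether the Week 48 limit truncates the 10-week follow-up. State which window applies to the PCSA tables. The related commitment, "Listing of PCSAs during the overall study period will be provided", takes its end from the same 7-day rule if the treatment-emergent period is meant.

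The cost is one paragraph and a re-flagging of AEs already collected. With 10 weeks as the main window, TEAE counts may rise, some of the added events will be unrelated to dosing, and post-dose windows will be unequal in the placebo-controlled tables. The supplementary 7-day table addresses the last of these.

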4.2 PARTICIPANT DISPOSITION

For participant study status, the total number of participants in each of the following categories will be presented using a summary table:

- Nonrandomized but treated participants
- Randomized participants
- Randomized but not treated participants
- Randomized and treated participants
 - Participants who completed the double-blinded, placebo-controlled study treatment period as per protocol
 - Participants who are ongoing the double-blinded, placebo-controlled study treatment period as per protocol
 - Participants who did not complete (eg, treatment early discontinuation) the double-blinded, placebo-controlled study treatment period as per protocol
 - Reasons for treatment discontinuation during the double-blinded, placebo-controlled study treatment period
 - Specified reason for treatment withdrawal by participant during the double-blinded, placebo-controlled study treatment period
 - Participants who completed the open-label extension study treatment period as per protocol
 - Participants who are ongoing the open-label extension study treatment period as per protocol
 - Participants who did not complete (eg, early treatment discontinuation) the open-label extension study treatment period as per protocol
 - Reasons for treatment discontinuation during the open-label extension study treatment period
 - Specified reason with treatment withdrawal by participant during the open-label extension study treatment period
 - Participants who completed the study
 - Participants who withdraw from study
 - Participants who withdraw from study by main reason of study discontinuation
 - Status at last study contact

For all categories of participants (except for nonrandomized categories) percentage will be calculated using the number of randomized participants as the denominator. Reasons for treatment discontinuation will be also provided.

